4.3 Baseline Monitoring

Once patient is enrolled, baseline monitoring will begin. The following shall be done:

- Collect a medical history
- Perform a cardiovascular exam
- Collect vital signs (heart rate-HR, blood pressure-BP, respiratory rate-RR), NYHA classification, height
- Administer KCCQ and EQ5D assessments
- Collect baseline blood labs (See **Appendix A**).
- Echocardiogram (for the baseline echocardiogram, an echocardiogram taken during the current hospitalization may be used if the required parameters are recorded and no clinically significant changes are suspected from time of the echocardiogram to the baseline visit)

Echocardiogram parameters to be recorded: severity of AR, TR and MR, EF, LVESV, LVEDV, LVEDD, LVESD, CO, SV, LA diameter, TAPSE, and RVIDD. The selection of the echocardiogram technique and views are left to the

^x If the patient has had imaging within the last 12 months, this can be used in lieu of repeating the imaging if no clinically significant change is suspected.

institution. A report should be generated and kept as source documentation. Baseline assessments will be made in accordance with the schedule of assessments in **Appendix A**.

In addition to baseline monitoring, the following shall be done:

- Urinary collection device placement at least 12 prior to implant
 - Begin careful fluid intake and output (I/O) monitoring starting at least 6 hours prior to Aortix implant)
- Document current renal and cardiovascular medications
 - Cease to adjust diuretics and inotropes 12 hours prior to Aortix implant

The following categories of medications should be recorded, at a minimum: ACE inhibitor, ARNI, angiotensin receptor blocker, antiarrhythmic, beta blocker, digoxin, diuretic, inotrope, nitrate, MRA, SGLT2, thiazide diuretic, nitroprusside. Medication dose changes will be tracked through the 72 hour/discharge visit. Medications at the follow-up will also be recorded.

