After signing informed consent, a urinary collection device will be placed, if not already present. A Foley catheter is recommended, but an external urine collection device may be used per institution requirements. The urine collection device will be placed (do not measure the urine collected during catheter placement) at least twelve (12 hours) before the Aortix Pump placement. If a urinary collection device is already in place, urine should be discarded. Output and intake should be strictly observed starting twelve hours prior to the scheduled implant. The urine collection device and the strict ins/outs monitoring will continue until the Aortix pump is retrieved. The first measurement of intake and output should occur at least six hours prior to Aortix placement and should be recorded every two hours until the pump is turned on. Measurements will occur at the frequency outlined in **Appendix A**.

Fluid ins should be monitored (IV and Oral) for the entire duration the urine collection device is in place with final measurements taken at the time of device retrieval.

Patients will receive standard medical therapy throughout the study. Patients should be on optimized medical therapy prior to being considered for Aortix Pump placement. To characterize the effect of the experimental device, physicians should not adjust the diuretic or inotrope dosing regimen during the twelve (12) hours prior to or the twelve (12) hours after Aortix Pump placement, unless medically necessary. **Diuretics and inotropes should not be adjusted for twelve (12) hours after the Aortix pump is turned on, however, after that point, while the Aortix pump is running, cessation of medications or down titration of diuretics, inotropes or other medications are allowed.** Adjustments of medical therapy can otherwise be made at any point during the study period at the discretion of the treating physician. All medications and medications adjustments will be captured on eCRFs.

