* Urine collection device should be inserted at least 12 hours before pump implant. Urine collection device may be removed at time of pump retrieval. Urine output measurement should exclude volume collected as part of urine collection device placement procedure. Fluid ins should be monitored (IV and Oral) for the entire duration the urine collection device is in place with final measurements for UOP and fluids in at the time of removal of the urine collection device. The “Day of Implant (Pre-implant)” UOP measurements should be taken every 2 hours before the pump is turned on. The first measurement of intake and output should occur at least six hours prior to Aortix placement and should be recorded every two hours until the pump is turned on.

** Cardiac Output (CO) and Cardiac Power Output (CPO) will be calculated by the sponsor. CPO parameters to be collected: SaO₂ (as measured by pulse oximeter), SvO₂ (as measured on mixed venous gas from PA catheter), hemoglobin (from CBC), blood pressure (to calculate MAP), weight, height, and heart rate.

HR, BP, PCWP, CVP and PAP – these values should also be collected any time the speed of the pump is adjusted. For PCWP it should be within 2 hours (+/- 30 min) of a speed change. For HR, BP, CVP and PAP it should be within 1 hour (+/- 30 min) of a speed change.

*** For United States patients, hospital billing information will be collected post-patient discharge.

^β Data collection at this time point is optional. Urine Output and Fluids IN required post device retrieval ONLY if urine collection device is still in place.

**** All heart failure and renal medications/medication adjustments should be recorded from baseline to discharge/72 hours post-device retrieval (whichever is first). At the 30 day follow-up, current medications should be recorded. Medication changes between discharge/72 hours post-device retrieval and follow-up do not need to be recorded.

⌚ 2 hours from time pump turned on during the deployment procedure.

◆ First measurement should be made 24 hours after pump is turned on. Subsequent every 24 hour measurements can be made during daily rounds or another convenient time as long as the first every 24 hour measurement is made at least 12 hours after the initial measurement 24 hours after the pump is turned on.

Hemodynamics Data Collection

Category	Pre-Therapy		Aortix Therapy								Post-Therapy		

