7.8.3.1 Fluid Intake / Urine Output

Cumulative Fluid Intake / Urine Output (mL) will be analyzed starting from the baseline measurement until Aortix retrieval. At each post-implant timepoint cumulative Fluid Intake / Urine Output (mL) will be defined as the total sum across all timepoints until corresponding post-implant timepoint. Cumulative Net Loss (mL) will be defined as the difference between Urine Output and Fluid Intake. Cumulative Fluid Intake, Urine Output and Net Loss will be presented graphically measurement from the baseline until Aortix retrieval by patient for As-Treated and PSC populations.

Hourly rate (mL/h) of Fluid Intake / Urine Output / Net Loss during Aortix therapy will be defined as cumulative Fluid Intake, Urine Output and Net Loss from baseline till the last pre-retrieval timepoint available divided by the number of hours (h) from baseline timepoint measurement till the last pre-retrieval timepoint available.

Baseline hourly rate (mL/h) of Fluid Intake / Urine Output / Net Loss will be defined as of Fluid Intake / Urine Output / Net Loss ([Urine Output] - [Fluid Intake]) from the last pre-baseline measurement to baseline divided by the number of hours (h) from the corresponding last pre-baseline timepoint till baseline.

Hourly rate of Fluid Intake / Urine Output / Net Loss at Baseline, during Aortix therapy and corresponding change from Baseline will summarized with descriptive statistics for As-Treated population.

Boxplots of Hourly rate of Fluid Intake / Urine Output / Net Loss will be provided by subgroup and overall to compare hourly rate during Baseline with hourly rate during Aortix therapy for As-Treated population.

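### The baseline urine rate rests on one interval of about 2 h, although the protocol collects at least 6 h before implant; the therapy rate also appears to start before the pump is on

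*SAP*

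**What the plan says.** SAP 7.8.3.1 defines the baseline hourly rate as the volume "from the last pre-baseline measurement to baseline divided by the number of hours (h) from the corresponding last pre-baseline timepoint till baseline". The rate during therapy is the cumulative volume from baseline, divided by the hours "from baseline timepoint measurement till the last pre-retrieval timepoint available". Both rates and the "corresponding change from Baseline will summarized with descriptive statistics for As-Treated population".

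The protocol collects more than one pre-implant interval. Section 4.3 states: "The first measurement of intake and output should occur at least six hours prior to Aortix placement and should be recorded every two hours", continuing until pump-on. The Appendix A footnote repeats that "UOP measurements should be taken every 2 hours before the pump is turned on". Section 4.3 also says "Output and intake should be strictly observed starting twelve hours prior to the scheduled implant", whereas its bulleted list says "Begin careful fluid intake and output (I/O) monitoring starting at least 6 hours prior to Aortix implant". To isolate the device effect, "physicians should not adjust the diuretic or inotrope dosing regimen during the twelve (12) hours prior to or the twelve (12) hours after" pump placement, unless medically necessary.

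The endpoint itself (Protocol 3.3.3, SAP 5.3) compares the rate before the pump with the rate over therapy and sets no length for the baseline. SAP 7.14 declares one change for this endpoint, the end of the therapy window. It mentions neither the baseline window nor the start of therapy.

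**The concern.** There is no control arm, so the pre-implant rate carries half of every comparison on this endpoint. The protocol sets up a stable run-in of up to 12 h with diuretic and inotrope dosing left unchanged, and the SAP then uses only the last reading interval. Urine flow over 2 h is erratic. Protocol section 7 says that each patient's data are reviewed individually, so noise in one patient's baseline is not averaged away there. SAP 6.2 also splits summaries into HFrEF and HFpEF, where numbers are smaller.

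The second issue is the start of the therapy window. Appendix A marks fluid intake and output on the day of implant (pre-implant) and not in the baseline-monitoring column, and Protocol 4.4.1 lists them before deployment. On that reading the fallback in SAP section 4 applies: baseline is the last value before the implantation procedure, and the therapy rate then includes time with the pump off. Protocol 4.3, headed Baseline Monitoring, also describes readings up to pump-on, so the main clause of SAP section 4 could apply instead. The SAP does not say which.

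**Working it through.** The plan states no SD, effect size, alpha or power for urine output, so it has no figure to reproduce.

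**Share of the baseline used.** At 2-h spacing, 6 h gives 6/2 = 3 intervals and 12 h gives 12/2 = 6. The SAP uses one: 1/3 of the minimum, or 1/6 of a full 12 h. The 2 h is inferred from the protocol's schedule; the SAP gives no length.

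**Worked patient (assumed volumes).** Three 2-h volumes of 300, 200 and 100 mL give 100/2 = 50 mL/h by the SAP rule and 600/6 = 100 mL/h over 6 h. The same volumes in reverse order give 300/2 = 150 against 100. Let the true on-pump rate be 150 mL/h for 48 h, after a 2-h off-pump gap at 100 mL/h. The SAP therapy rate is (48×150 + 2×100)/50 = 148 mL/h. The SAP change is then 148 − 50 = +98 or 148 − 150 = −2 mL/h. With a 6-h baseline and a pump-on start it is 150 − 100 = +50 in both cases. The gap accounts for only 2 mL/h of this.

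**SD of a patient's change.** Assumptions: mean 100 mL/h; CV 50%, so SD 50 mL/h per 2-h reading; first-order autoregressive correlation ρ between successive readings; one 2-h gap; no device effect. SD = 50·√(w′Rw), where R is the correlation matrix and w is −1/n on the n = 1, 3 or 6 baseline readings and +1/m on the m therapy readings. The covariance between baseline and therapy is therefore included. m = 24 for 48 h (Protocol 4.5.2.1, minimum of two days at initial speed) and m = 84 for 168 h (Protocol 4.5, seven days tested).

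| Therapy | ρ | 2 h | 6 h | 12 h | Reduction, 6 h / 12 h |
|---|---|---|---|---|---|
| 48 h | 0 | 51.0 | 30.6 | 22.8 | 40% / 55% |
| 48 h | 0.5 | 51.9 | 42.0 | 35.2 | 19% / 32% |
| 48 h | 0.8 | 51.0 | 48.0 | 45.4 | 6% / 11% |
| 168 h | 0 | 50.3 | 29.4 | 21.1 | 42% / 58% |
| 168 h | 0.5 | 50.6 | 40.0 | 32.5 | 21% / 36% |
| 168 h | 0.8 | 50.6 | 46.7 | 42.9 | 8% / 15% |

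The SDs scale with the CV. At 48 h and ρ = 0.5 they are 31.1, 25.2 and 21.1 for a CV of 30%, and 72.6, 58.8 and 49.2 for 70%.

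**Group mean.** The 95% half-width is t(0.975, N−1)·√(SD² + 50²)/√N, with an assumed between-patient effect SD of 50 mL/h and 48 h of therapy.

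| N | ρ | 2 h | 6 h | 12 h |
|---|---|---|---|---|
| 30 | 0 | 26.7 | 21.9 | 20.5 |
| 30 | 0.5 | 26.9 | 24.4 | 22.8 |
| 30 | 0.8 | 26.7 | 25.9 | 25.2 |
| 15 (assumed even split) | 0 | 39.6 | 32.5 | 30.4 |
| 15 | 0.5 | 39.9 | 36.2 | 33.9 |
| 15 | 0.8 | 39.6 | 38.4 | 37.4 |

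**Bias.** The mean absolute change is unbiased whatever the baseline length. A mean relative change is not, because a noisy baseline sits in the denominator. In 200,000 simulated no-effect patients (lognormal, same CV and ρ), baselines of 2, 6 and 12 h give mean relative changes of +25%, +8%, +4% (ρ = 0); +24%, +15%, +10% (0.5); and +21%, +18%, +15% (0.8).

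**Off-pump time.** If L hours at the baseline rate precede H hours on the pump, a true change shrinks by L/(L+H). For an assumed L of 1 to 4 h this is 1/49 = 2.0% to 4/52 = 7.7% at H = 48, and 1/169 = 0.6% to 4/172 = 2.3% at H = 168.

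**The case against.** The endpoint is descriptive. Urine output is left out of the Wilcoxon comparisons in SAP 7.8.3, has no success threshold, and the sample size was not statistically derived. The protocol fixes no baseline window, so the SAP does not contradict it, and the interval nearest implant is a recognisable choice. All of this stands and limits the point to precision. It does not supply a reason to set aside required data, and the SAP gives none.

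The largest gains need zero serial correlation and apply per patient. On the group mean at N = 30, a 6-h baseline narrows the half-width by 18%, 9% or 3% across the three correlations. That also stands: the gain runs from material to small.

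The 2-h length is inferred, and the CRF is not available. If fewer pre-implant readings were stored, the single interval would be longer. The SAP plans no relative change for urine; Protocol section 7 names relative changes only as an example, so that bias is conditional.

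The off-pump gap depends on which reading counts as baseline. With readings due every 2 h until pump-on it may not exceed about 2 h (2/50 = 4.0% at 48 h), and the first-in-human deployments took under 10 minutes (Protocol 1.2). The dilution also works against the device. It is small, but the SAP still needs to name the reading.

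Listing 16.2.11.2.1 should let a reader recompute a longer baseline. The cumulative plots start at baseline, so they do not show the pre-implant course. The 6-h and 12-h statements in Protocol 4.3 can be read as compatible, since 12 h satisfies a minimum of 6 h, but one wording would remove the doubt.

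**Conclusion.** The concern holds and should be fixed. As written, SAP 7.8.3.1 uses one interval and leaves out at least two thirds of the pre-implant urine record that the protocol requires, for the only comparator of a primary effectiveness endpoint, without declaring or justifying it. The cost is precision in the absolute change. Under the stated assumptions, the SD of a patient's change at 48 h could be 6% to 40% lower with a 6-h baseline and 11% to 55% lower with 12 h. The CV, the serial correlation and the between-patient SD are assumptions, because the documents give none. Bias arises only through off-pump hours in the therapy window (about 2% to 8% shrinkage at 48 h for 1 to 4 h) or if a relative change is reported. The reading of the text is secure; the size of the gain depends mainly on the serial correlation.

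**What to change.** 1. In SAP 7.8.3.1, define the baseline rate as all urine recorded from the start of strict pre-implant collection (at least 6 h, up to 12 h) to the last pre-implant reading, divided by the actual hours. List those hours per patient. The last-interval rate can be kept as a sensitivity analysis.
2. Start the therapy window at pump-on or the nearest reading, and state which reading is baseline for fluids. State also that the cumulative sum begins after that reading. If the 2-h volume logged at the baseline reading entered the sum while the hours started there, a patient with no change over 50 h (48 h on the pump plus a 2-h gap) would show 52/50, an inflation of 4%.
3. Record both definitions in SAP 7.14.
4. Editorial: align SAP 5.3 and 7.8.3 with the end rule already in 7.14 and 7.8.3.1. Say in 7.14 which CRF form lacks the congestion-target timepoint, since Protocol 4.5.3 requires fluids then. If that reading exists, report the rate up to it as a sensitivity analysis. Reconcile the two statements in Protocol 4.3 on when intake and output monitoring begins.

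The cost is SAP wording and a small programming change. Pump-on time already anchors the 2-h post-implant visit in Appendix A. The downsides are that baseline length will vary between patients (about 6 to 12 h), that it falls back to about 6 h if the start of the first collection was not recorded, and that the gain is small if serial correlation is high.

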7.9 Safety and Additional Data Analysis

7.9.1 Adverse Events (AE)

CEC classification will be used for the analysis of AEs. Additional overall summary and listing for the Investigator's classification of AEs will be provided.

TEAEs will be defined as AEs not present prior to the start of study procedures, or AEs present before study treatment that worsened after implantation. If a partially missing date or time of onset allows the possibility that an AE may be a TEAE it will be presumed to be a TEAE.

AEs will be summarized by subgroup and overall by the number and percentage of patients who experienced at least one AE of any of the following types: any AE, any TEAE, any TEAE Related to Aortix Therapy, any TEAE Related to Aortix Procedure(Aortix Implant Procedure or Aortix Retrieval Procedure), any TEAE Related to Study Required Procedures, any serious TEAEs, any SAE, any SAE Related to Aortix Procedure, any SAE leading to death, any unanticipated adverse device effect.

AEs will be summarized by categories for the ITT population.

TEAEs will be summarized by category and by relationship for the ITT population.

Listings of all AEs will be provided for the All Enrolled population.

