4.2 Enrollment

The patient is considered enrolled in the study when they sign the informed consent and before imaging screening is initiated. Following Informed Consent, imaging of ilio-femoral and aortic anatomy will be obtained to verify appropriate diameter and evaluate for any abnormalities that would preclude device placement. Imaging modality is up to the site, but one or more of the following modalities are recommended: non-contrast CT, intravascular ultrasound (IVUS) or external arterial ultrasound. Magnetic Resonance Angiography (without contrast) or CO2 angiography may also be considered.^x

If not done previously, PAC placement can occur any time after informed consent is signed and before device placement to confirm inclusion criterion for objective measure of congestion. Alternatively, PAC placement can occur in the cath lab before the Aortix device implant procedure.

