4.8 Follow-Up

Patients with the pump implanted will be followed for adverse events for 30 days (± 7 days) post device retrieval. If implanted patients are still hospitalized at 30 days due to an adverse event relating to the device or any study related procedures, they must be followed until resolution of the adverse event, resolution with sequelae, or until a terminal event. Protocol required data collection for patients with the pump implanted will be for 30 days post device retrieval (± 7 days) per **Appendix A**.

The following data will be collected:

- NYHA classification
- Cardiovascular exam (edema, pulmonary auscultation, weight),
- Vital signs (HR, BP, RR)
- Dyspnea evaluation
- KCCQ, EQ5D
- Document current cardiovascular/renal medications and adverse events
- Blood and urine labs per **Appendix A**

Patients that have an attempted implant but do not have the pump implanted will be followed for adverse events for 30 days (± 7 days) post attempted implant. If attempted implant patients are still hospitalized at 30 days due to an adverse event relating to the device or any study related procedures, they must be followed until resolution of the adverse event, resolution with sequelae, or until a terminal event.

Terminal events are death, LVAD implantation, heart and/or kidney transplantation, dialysis, ultrafiltration or CRRT.

Patients who are enrolled and undergo anatomy screening and/or invasive hemodynamic measurements who do not have an attempted implant will be followed for adverse events for 7 days (\pm 2 days) post anatomic screening or invasive hemodynamics (whichever is later) or until hospital discharge, whichever is first.

Every attempt should be made to perform follow-up visits in person. Should extenuating circumstances (e.g., COVID-19 global pandemic travel restrictions) impact a site's ability to perform follow-up visits in person, notify the sponsor and make every attempt to collect the protocol required data via other means (e.g., telephone, video conference, blood and urine labs at a non-hospital lab).

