(Medtronic CoreValve Revalving System – 18F delivery sheath) to 15% (Edwards SAPIEN valve – 22-24F delivery system) of subjects.²⁷ Although the Aortix Pump may be deployed percutaneously by an interventional cardiologist, for this pilot study, the physician may obtain direct vascular access to the femoral artery via cutdown and direct visualization. During vascular access, ultrasound guided placement, micropuncture needles, and microangiography may be considered to ensure proper placement of the guidewire and minimize vascular injury and bleeding.

Upon retrieval of the Aortix Pump, the femoral artery may undergo primary surgical closure. Additionally, at follow-up visits, the femoral artery and descending aorta may be non-invasively imaged to ensure vessel patency and structural integrity.

Vascular imaging, clinical monitoring, and clinical mitigation steps will be used to minimize the occurrence of these risks. The likelihood of these risks is unknown, as this is the first introduction of the investigational Aortix Pump into a human population with a duration of treatment more than 90 minutes. However, bench-top testing and large animal studies have demonstrated that the Aortix Pump can be safely implanted and retrieved after multiple days of use. Simulated use testing has demonstrated acceptable performance of the device under clinical use conditions and/or repeated use.

There may be other, unknown complications that may occur as a result of this procedure. If these or any of the above complications occur, they may lead to repeat or prolonged hospitalization, repeat procedures, emergency surgery, other emergency procedures, or, in rare cases, death. The study doctor and/or the research staff will make every effort to minimize additional risks.

There are also risks associated with the pulmonary artery catheter insertion procedure, which is non-investigational, but required by the study protocol. The most common risks are bruising at the site of the PAC insertion, excessive bleeding and vein injury or tear. Pneumothorax can also occur as a result of a puncture to the lung. This is more common when the catheter is inserted into the neck or chest veins.

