For this clinical study, adverse events will be collected post informed consent when invasive or non-standard-of-care screening begins (i.e. imaging or invasive hemodynamics). For safety reporting, all adverse events will be reported until the patient exits the study. Any unresolved procedural or device related adverse events that are still ongoing past study exit will be reported as being unresolved or unresolvable.

Enrollment will pause if any of the following serious, procedure related adverse events occur:

- Death (Aortix procedure related only)
- Aortic Injury Requiring Surgical Intervention to Repair (Aortix procedure related only)

Enrollment will be paused until the event can be evaluated and discussed with regulatory agencies if appropriate and approval is granted to continue enrollment.

For purposes of this study, minor clinical changes which would normally occur for this patient during the course of having heart failure which are not related to the device, the procedure or the therapy, need not be reported. Examples include but are not limited to ongoing poor appetite, weakness or fatigue. Investigator discretion is expected. If unsure, report as an adverse event.

It is anticipated that due to underlying baseline conditions, all laboratory values may not remain in the range of normal for a given participant. Investigator discretion is required to determine if a laboratory value that remains out of range is associated with an untoward clinical finding that should be reported as an adverse event.

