2.3 Determination of Sample Size

The sample size of up to thirty (30) implanted patients is based upon industry standards for early stage studies of medical devices; the sample size was not statistically derived.

The study will provide data to be used for demonstrating initial device safety and effectiveness in this patient population, as well as providing input for design of future clinical studies of the device. It is estimated that approximately 50% of patients enrolled may not receive the pump due to anatomical requirements or right heart PA catheterization requirements not being met or inability to implant the pump. Therefore, we plan to enroll up to 60 patients to yield 30 implanted patients.

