6.1.2 Intent-to-Treat (ITT) Population

The ITT population will be defined as all enrolled patients that have an attempted implant whether or not successful. This population will be used for demographic and partial safety analyses.

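### Adverse events from study-required screening procedures enter no adverse-event summary table or rate when the patient never reaches an implant attempt

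*SAP*

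**What the plan says.** Enrollment precedes the screening procedures. Protocol 4.2: "The patient is considered enrolled in the study when they sign the informed consent and before imaging screening is initiated". Safety data start soon afterwards. Protocol section 6 (opening text) says that "adverse events will be collected post informed consent when invasive or non-standard-of-care screening begins (i.e. imaging or invasive hemodynamics").

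The protocol treats these procedures as a source of risk. Section 5.2: "There are also risks associated with the pulmonary artery catheter insertion procedure, which is non-investigational, but required by the study protocol". It then names bruising, excessive bleeding, vein injury and pneumothorax. Section 4.8 provides safety follow-up for patients who stop at this stage: "Patients who are enrolled and undergo anatomy screening and/or invasive hemodynamic measurements who do not have an attempted implant will be followed for adverse events". The period is 7 days (± 2) after the later screening procedure, or until discharge if that comes first.

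The SAP sets the populations. Section 6.1.2: "The ITT population will be defined as all enrolled patients that have an attempted implant whether or not successful". Section 7.9.1: "AEs will be summarized by categories for the ITT population"; treatment-emergent events follow the same rule. That section also plans a row for treatment-emergent events related to procedures that the study requires, in a sentence that names no population. For All Enrolled it promises listings only. SAP 6.1.1, however, assigns All Enrolled to part of the safety analysis as well as to disposition and eligibility.

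**The concern.** The patients for whom a row on study-required procedures matters most are those harmed by screening. If a bleed or pneumothorax at catheter placement cancels the implant, the patient never enters ITT and leaves both the numerator and the denominator of that row. The exclusion depends on the event being counted, so it can be informative.

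At stake is a usable count, with a denominator, of what screening costs patients. SAP 2.3 says the study should provide input for the design of later studies, and those would probably need similar screening. Protocol 3.3.4 also lists the rate of all adverse events without restricting it to attempted implants, and the primary serious-event endpoint in Protocol 3.3.1 runs from enrollment.

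**Working it through.** **Step 1: which population each safety output uses (SAP Appendix 1 and section 7).**

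| Output | Population |
|---|---|
| Primary safety, Table 14.2.1.1 | As-Treated |
| Adverse events, CEC and investigator, 14.3.1.1.1 and 14.3.1.1.2 | ITT |
| Treatment-emergent events, 14.3.1.2 and 14.3.1.3 | ITT |
| Serious events, 14.3.1.4 | ITT |
| Unanticipated device effects, 14.3.1.5 | ITT |
| Deaths, 14.3.2 | ITT (SAP 7.12 text: As-Treated) |
| Death listing, 16.2.13.2 | ITT |
| Adverse-event listings, 16.2.7.1 and 16.2.7.2 | All Enrolled |
| Disposition, 14.1.1.1 | All Enrolled |

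The number of safety tables on All Enrolled is zero. The safety role that SAP 6.1.1 gives that population is met only by listings. The row on study-required procedures has no stated population in the text, but every table that could hold it is ITT.

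**Step 2: how many patients can fall outside ITT.** Inputs: 30 implanted and up to 60 enrolled (both documents); non-implant share 50% (SAP 2.3: "approximately 50% of patients enrolled may not receive the pump") or 33% (Protocol section 7). Enrollment needed = implanted / (1 − share).

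- SAP: 30 / (1 − 0.50) = 60. This reproduces the planned 60. Not implanted: 60 − 30 = 30.
- Protocol: 30 / (1 − 0.33) = 44.8, about 45. This does not reproduce 60. Not implanted: 45 − 30 = 15.

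Both counts are upper bounds. The stated reasons for non-implant include inability to implant the pump, and failed attempts are already in ITT.

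**Step 3: enrolled does not mean exposed.** Under Protocol 4.2 the catheter is placed after consent only if not placed before, and placement may wait until the cath lab. A footnote to sections 4.2 and 4.3 lets imaging from the last 12 months replace study imaging. A patient who fails on anatomy may never have a study catheter. The number exposed but not attempted is therefore below the counts in Step 2 by an amount the documents do not give.

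**Step 4: chance that the gap matters.** The documents give no complication rate, so p is an assumption, per exposed patient without an attempt. The chance of at least one untabulated event among m such patients is 1 − (1 − p)^m.

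| p | m = 15: expected, chance | m = 30: expected, chance |
|---|---|---|
| 2% | 0.3, 26.1% | 0.6, 45.5% |
| 5% | 0.75, 53.7% | 1.5, 78.5% |
| 10% | 1.5, 79.4% | 3.0, 95.8% |

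These use the upper-bound counts, so they are themselves upper values for each p.

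**Step 5: direction of any bias.** With a events in n attempted patients and b events in m patients without an attempt, the planned row shows a/n and the full rate is (a + b)/(n + m). The planned row is lower only if a/n < b/m. Take a hypothetical 3 complications with n = m = 30, pretending that all 60 were exposed:

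- 2 of the 3 cancel the implant: 1/30 = 3.3% against 3/60 = 5.0%, so the planned row is lower.
- 1 of the 3 cancels: 2/30 = 6.7% against 3/60 = 5.0%, so the planned row is higher.

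The sign depends on how often a complication cancels the implant, which the documents do not say.

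**The case against.** The strongest reply is that nothing is lost. All clinical events go to the CEC (Protocol 6.3), both adverse-event listings cover All Enrolled, and an exit can show as a screen failure or discontinuation reason in disposition. With at most 60 patients, a reader could count the events by hand. The protocol says each patient's data will be reviewed individually, the sample size was not statistically derived, and no safety test is planned. The safety objective concerns delivery, use and retrieval of the pump, and the catheter is not investigational. All of this stands, and it limits the consequence. It does not remove the gap: a listing gives no denominator or rate, and the SAP itself plans a row on study-required procedures.

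A reader might infer more than the documents support:

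- That the events vanish from the report. They do not; only adverse-event summary tables and rates omit them.
- That the planned rate is biased low. Step 5 shows that it could go either way, and the shorter follow-up without an attempt would also pull an all-patient rate down.
- That half of the exposed patients are discarded, or that a 0/60 confidence limit applies. Both treat every enrolled patient as exposed.
- That the sponsor chose to leave these patients out of the safety summaries. SAP 6.1.1 points the other way; the table list simply does not carry it through.

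**Conclusion.** The gap is real and small. As the SAP stands, an adverse event from the protocol-required catheter or study imaging in a patient without an implant attempt enters no adverse-event summary table or rate, including the row meant for such events. At most about 30 of 60 enrolled patients (SAP share) or 15 of 45 (protocol share) are concerned, fewer to the extent that some failures are aborted attempts and some patients had no study procedure. Selection out of ITT can be informative, but the net direction and size of bias cannot be determined.

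This rests on Appendix 1 fixing the population where the 7.9.1 sentence is silent, and on reading an attempted implant as something later than screening. The documents do not define the term. For a catheter placed in the cath lab just before implant, it is unclear whether a complication puts the patient in ITT. No effectiveness analysis is affected. Severity: minor reporting improvement.

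**What to change.** Reconcile SAP 6.1.1 with Appendix 1 by adding one table to 7.9.1 and the table list: adverse events and serious adverse events, including deaths, related to study-required procedures. Its population is all enrolled patients who underwent study imaging or pulmonary artery catheter placement, split by implant attempted or not. Define an attempted implant in SAP 6.1.2, covering the case of a catheter placed in the cath lab. Footnote the follow-up: 7 days or discharge, whichever is first, without an attempt, against 30 days after the attempt or after retrieval. Keep the ITT tables for Aortix-related events.

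The cost is one table from adverse events already collected and listed, plus a flag for who had a study procedure, assuming the CRF records this. The drawback is that the two groups have unequal follow-up, so their rates should not be compared directly.
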